STUDY FLOW CHART	7
1. BACKGROUND	9
2. RATIONALE	10
3. THEORETICAL FRAMEWORK	10
4. RESEARCH QUESTION/AIM(S)	15
5. STUDY DESIGN/METHODS	16
6. STUDY SETTING	19
7. SAMPLE AND RECRUITMENT	20
8. ETHICAL AND REGULATORY COMPLIANCE	25
9. DISSEMINATION POLICY	28
10. REFERENCES	29
11. APPENDICES	34

ABBREVIATIONS

CI	Chief Investigator
CRF	Case Report Form
ICF	Informed Consent Form
ISF	Investigator Site File
NHS	National Health Service
NIHR	National Institute for Health Research
PI	Principal Investigator
REC	Research Ethics Committee
SGUL	St Georges, University of London
JRES	(St Georges) Joint Research and Enterprise Services
WHO	World Health Organisation
ROM	Rupture of membranes
EOS	Early onset sepsis
LOS	Late onset sepsis
PCR	Polymerase chain reaction
LRS	Low resource setting

KEY STUDY CONTACTS

Chief Investigator	
Principal Investigator (In-Country)	
Study Co-ordinator	
Sponsor	St George's, University of London
Funder(s)	CREATE (Africa Health Research Training Programme) Wellcome Trust
Key Protocol Contributors	

STUDY SUMMARY	
Study Title	Using machine learning to model early-onset neonatal sepsis risk in Uganda
Internal ref. no. (or short title)	NeoRisk
Study Design	Observational
Study Participants	Neonates born at ≥ 34 weeks' gestational age at Kawempe Hospital in Kampala, Uganda (Phase 1) or Sally Mugabe Central Hospital in Harare, Zimbabwe (Phase 3)
Planned Size of Sample (if applicable)	1600 (Phases 1+2), 900 (Phase 3)
Follow up duration (if applicable)	1 month post-delivery
Planned Study Period	September 2023-May 2024
Research Question/Aim(s)	
1. Determine antenatal and perinatal factors associated with early-onset neonatal sepsis in low-resource settings, as diagnosed by a blood culture or a senior clinician2. Measure the strength of association between the above factors and early-onset neonatal sepsis3. Combine the above risk factors into a risk stratification model for early-onset neonatal sepsis using machine learning techniques
FUNDING AND SUPPORT	
FUNDER(S)	FINANCIAL AND NON FINANCIAL SUPPORT GIVEN
CREATE PhD Programme	

ROLES AND RESPONSIBILITIES OF STUDY MANAGEMENT COMMITTEES/GROUPS & INDIVIDUALS

The study has been discussed with the Community Engagement team at Makerere University-Johns Hopkins University Research Collaboration in Kampala, Uganda, which works with clinical studies at Kawempe Hospital.

The team have provided feedback on the acceptability of this study, including on the taking of a blood culture sample, recruitment strategy, and on development of patient information resources.

[figure not shown]
The study team will continue to work closely with the Community Engagement team throughout the study to ensure its acceptability and to disseminate research findings to the community and relevant stakeholders.

PROTOCOL CONTRIBUTORS

No funders have been involved in study design and no funder will be involved in conduct, data analysis and interpretation, manuscript writing, or dissemination of results. The funder does not control the final decision regarding these aspects.

[figure not shown]
As above, the protocol has been designed in collaboration with the Community Engagement team who represent members of the community, patients, and carers.

STUDY Schematic: Phase 1 (Uganda)

Phase 2 comprises analysis and modelling of data collected in Phase 1.

STUDY Schematic: Phase 3 (Zimbabwe)

Using machine learning to model early-onset neonatal sepsis risk in Uganda (NeoRisk)

Using machine learning to model early-onset neonatal sepsis risk in Uganda (NeoRisk)

STUDY PROTOCOL

Using machine learning to model early-onset neonatal sepsis risk in Uganda

1 BACKGROUND

Sepsis is a leading cause of neonatal mortality worldwide(1), affecting 39.3 per 1000 live births in low- and middle-income countries(2). Mortality from early-onset sepsis can be reduced with prompt, correct treatment with antibiotics(3); therefore, identifying those at risk early is crucial. The sepsis rate in Uganda is high, with an incidence of 68 per 1000 live births, and is highest in hospital facilities(4).

Antibiotics are recommended for neonates with specific risk factors for sepsis, and those with signs of illness, including poor feeding and drowsiness(5). However, many low-resource settings diverge from the World Health Organization (WHO)'s recommended regimens, often due to antimicrobial resistance (5–7) or drug availability(8). Ideally, antibiotics should be given within an hour of birth in cases of suspected early-onset sepsis, which accounts for almost ¾ of sepsis cases in Uganda(4,9).

Additionally, risks of antimicrobial resistance are increasing. Neonates with sepsis in low- and middle-income countries show significant rates of resistance to the extent that the majority of proven infections are resistant to first and second line WHO-recommended antibiotics(10,11). Mortality from sepsis is double with resistant versus sensitive organisms(12). Previous studies in Kampala have shown high rates of resistance to first-line antibiotics(13). Prolonged antibiotic therapy without proven infection is associated with morbidity and mortality in preterm infants, and may affect normal flora and immunity(14,15). Therefore, antimicrobial stewardship is vital for low-resource settings. Accurate, early identification of at-risk neonates allows the benefits of early treatment whilst minimising the harms of overtreatment, and unnecessary admission.

Risk stratification systems are established tools in medicine, including in sub-Saharan Africa(16,17), to predict mortality in paediatric inpatients(18) and neonates(19), but previously tested systems for prediction of neonatal sepsis in low-resource settings show modest performance(20). This may be due to limited laboratory testing, so systems are built at least partially on clinician defined sepsis rather than the gold-standard of blood culture diagnosis(20). In high resource settings, risk stratification systems have focused on reducing overtreatment and antibiotic resistance(14,15,21). Neonatal sepsis risk calculators (a risk stratification system with a digital interface), such as the Kaiser Permanente (KP) Early-Onset Sepsis (EOS) calculator, have been adopted in the USA and UK(22). This calculator uses local incidence of EOS, gestational age, time from rupture of membranes (ROM) to delivery, highest maternal temperature during labour, maternal group B Streptococcus status, and type and timing of antepartum antibiotics(23).

In low-resource settings, the consequences of missing neonatal sepsis are more severe due to limited higher acuity care(24). Therefore, sepsis risk assessment in a low-resource setting should prioritise sensitivity over specificity, although prioritisation of limited resources for true cases is also helpful(25). Existing risk calculators may be inappropriate to use in a

Using machine learning to model early-onset neonatal sepsis risk in Uganda (NeoRisk)

low-resource setting; background incidence of EOS is much higher in these settings(1,2). Other clinical and non-clinical factors may mediate risk, such as HIV status or birth location. Few of the usual risk factor inputs are available in a low-resource setting. For example, without adequate antenatal care and imaging, gestational age may be uncertain, and without skilled birth attendants, duration of ROM may be unknown. Finally, diagnostic facilities for sepsis such as biochemical tests for inflammatory markers may be limited or unavailable. This makes identification of those at-risk using clinical factors, as opposed to laboratory testing, even more important. Additionally, lack of access to blood cultures has limited the ability of previous models to include this 'gold standard' of diagnosis in their modelling(20).

2 RATIONALE

Current risk stratification systems are not able to predict neonatal sepsis risk in a low-resource setting with sufficient accuracy, as outlined in section 1. Reliable prediction of neonatal sepsis risk would enable clinicians to prioritise early broad-spectrum antibiotics and close monitoring for the highest-risk neonates, reducing associated morbidity and mortality, and allow earlier discharge of low-risk neonates without antibiotic treatment, reducing the economic and psychological burden to families of remaining in hospital and antimicrobial overuse. In a wider context, the ability to predict sepsis risk more accurately would also aid the development of clinical pathways and service planning within maternity and neonatal services. Finally, the resulting model and code from this study could be used by other researchers in the future to model risk of other infective conditions, or neonatal sepsis in other settings.

To build a model for risk stratification, data are required that encompass not only a broad range of potential risk factors for sepsis, but also accurate outcome data confirming or refuting the diagnosis of sepsis. Previous attempts to create risk stratification systems have lacked blood cultures as the gold standard diagnostic method for sepsis(20), so this study will include a blood culture sample from every participant. This study will also include a range of patient-reportable potential risk factors to maximise the clinical utility of the model in the future.

3 THEORETICAL FRAMEWORK

Aetiology of neonatal sepsis

Neonatal sepsis is commonly defined as a severe systemic infection occurring in the neonatal period. Early-onset neonatal sepsis (EOS) refers to those infections presenting within 72 hours of life and is usually the result of vertical acquisition of the pathogen. This is in contrast to late-onset neonatal sepsis which presents after 72 hours of life usually results from horizontal acquisition of the pathogen (i.e. from the neonate's environment)(26).

Many risk factors are common to both early- and late-onset sepsis, but their importance differs for each of the conditions. EOS relates more to maternal risk factors(26–29), and LOS to neonatal factors(26,27,29). Environmental factors will also influence the risk of LOS, as they will affect the risk of horizontal transmission of pathogens(26,27). As this study aims to create a risk stratification system relevant for low-resource settings, it is important to consider patient-

Using machine learning to model early-onset neonatal sepsis risk in Uganda (NeoRisk)

reportable or easily measurable factors that may modify the risk of neonatal sepsis. These have been considered systematically by examining possible related maternal, neonatal, and environmental factors and their associations.

Patient-reportable risk factors

To assess many of the established risk factors for neonatal sepsis, mothers must receive skilled antenatal and delivery care; for example, a diagnosis of chorioamnionitis would require assessment by a midwife or doctor and may also require measuring of vital signs and laboratory tests to confirm the diagnosis. As the purpose of this project is to statistically model risk factors for early-onset neonatal sepsis with the aim to help inform clinical decision making in a low-resource setting, it is necessary to consider the association between neonatal sepsis and factors which are either patient-reportable or easily measurable without the need for laboratory or radiological services that may be unavailable in these settings.

Therefore, in designing the data collection instrument for this study, we have considered which patient-reportable factors might be strongly associated with the established sepsis risk factors above, and determined the following fields for data collection, listed in the table below:

Category	Risk factor	Data collection field	Established	Investigational
Maternal factors prior to pregnancy	Age	(years)	X	
	Tribe			X
	Medical comorbidities increasing infection risk			
	HIV		X	
	Chronic infection e.g. hepatitis, tuberculosis		X	
	Regular immunosuppressive medications e.g. steroids		X	
	Previous abdominal surgery			X
	Obstetric history		X	
	Number of previous pregnancies		X	
	Number of previous live deliveries			X
Low socioeconomic status	Number of previous neonatal deaths		X	
	Maternal and partner's occupation			X
	Location of dwelling			X
	Construction of dwelling			X
	Occupancy of dwelling, including number of adults, children, and animals			X

Using machine learning to model early-onset neonatal sepsis risk in Uganda (NeoRisk)

	Source of lighting		x
	Maternal and partner's educational level		x
	Cooking facilities at home e.g. open fire indoors, gas stove		x
	Access to refrigeration at home		x
	Food insecurity		x
	Presence or absence of debt		x
	Water, sanitation and hygiene	x	
	Type of sanitation available at home (type of toilet/latrine)		x
	Source of drinking water		x
	Access to handwashing facility at home		x
	Nutritional status	x	
	Mid upper arm circumference	x	
	BMI	x	
	Dietary quality		x
	Substance use	E.g. recreational drugs, smoking, alcohol	x
Maternal factors during pregnancy	Vaginal colonisation		x
	Abnormal discharge during pregnancy		x
	Vulval or vaginal discomfort/pruritus		x
	Dyspareunia or postcoital bleeding		x
	Regularity of menstrual cycle		x
	Urinary tract symptoms during pregnancy	x	
	Diarrhoea or vomiting during pregnancy	x	
	Access to sanitation at home		x
	Antibiotic use during pregnancy		x
	Invasive procedures during or prior pregnancy e.g. cervical cerclage, surgical termination of pregnancy		x
	Insufficient or late antenatal care		x
	Number of antenatal appointments attended		x
	Number of antenatal ultrasound scans		x
	Screening blood tests taken antenatally		x

Using machine learning to model early-onset neonatal sepsis risk in Uganda (NeoRisk)

Using machine learning to model early-onset neonatal sepsis risk in Uganda (NeoRisk)

Low APGAR scores		X	
Clinical signs of sepsis or meningitis within first 72h of life		X	
	Temperature instability	X	
	Poor feeding	X	
	Lethargy	X	
	Jaundice at <24h of life	X	
	Respiratory distress	X	
	Tachycardia	X	
	Tachypnoea	X	
	Poor perfusion	X	
	Abnormal tone	X	
Umbilical cord care	e.g. application of herbal remedies		X
Method of feeding	Breast versus formula	X	
	Water used to make up formula (e.g. filtered, tap)		X

Diagnosis of neonatal sepsis

The 'gold standard' for diagnosis of neonatal sepsis is widely considered to be a microbiological culture of neonatal blood(30), using at least a 1 ml sample(31). However, the proportion of neonatal patients with clinical signs of sepsis whose blood cultures are returned as negative can be significant, with studies reporting between 6 and 16 cases of 'culture-negative sepsis' for every culture-positive case(14). Therefore, although the use of blood culture is the gold standard, other diagnostic methods must be considered in order to capture all cases of neonatal sepsis and subsequently develop an accurate statistical model.

Various proxy biochemical and haematological markers of sepsis are commonly measured and used in clinical practice in high-resource settings, including C-reactive protein, procalcitonin, and full blood counts. These markers are all useful in making a diagnosis of sepsis and monitoring response to treatment, but none have sufficiently high sensitivity or specificity to be used in isolation(30). Additionally, in low-resource settings (including those settings in which this study will take place), access to consumables and laboratory facilities to measure these markers is unreliable. For this study, the use of additional biochemical and haematological markers has therefore been deemed to have limited usefulness in contributing to the statistical model, and so will not be used.

Clinical diagnosis of sepsis is challenging due to the nonspecific signs exhibited by neonates(32) and the lack of a universal definition of clinical sepsis(33). Signs of sepsis are also present in neonates without infection who are transitioning to extra-uterine life, or suffering from other conditions(32,34). However, given the near-universal availability of clinical diagnosis and the limitations of blood cultures to identify all cases of sepsis, we feel it is important to include clinical diagnosis of sepsis as a secondary outcome. Given the subjective nature of an individual clinician's diagnosis, we will also include established criteria for the diagnosis of sepsis that also assess the level of confidence in the clinical diagnosis, to reflect the spectrum of diagnostic certainty. We will therefore use the GAIA neonatal infection case definition criteria to assess cases, which are intended for international use(35,36).

Using machine learning to model early-onset neonatal sepsis risk in Uganda (NeoRisk)

Use of machine learning for risk stratification modelling

Machine learning is a field with increasing prominence, where computer systems are used to create algorithms to represent a data set(37). Evaluation of risk factors for neonatal sepsis could be achieved using traditional statistical techniques, as has been done for risk stratification models such as the Kaiser Permanente Sepsis Calculator(38). However, machine learning techniques allow increased flexibility and are better suited to factors with a non-linear relationship to the outcome(39), in addition to their ability to analyse large and complex data sets(40). Additionally, machine learning techniques may be able to discover novel associations and relationships that, although still requiring human validation as biologically plausible, may not have been discovered by traditional human-led analysis.

Therefore, a machine learning approach could enable the creation of a more accurate risk stratification model, making it the appropriate method to use for statistical analysis in this study. The success of machine learning methods is dependent on having sufficient data to train the model, and the ability to test it on external datasets. This has been accounted for in the design of this study by optimising the quality and accuracy of the training dataset (using a study site where blood culture results are reliably available), before testing the model in a second population to provide an external dataset.

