4.2 Outcome

- Primary outcome for Phase 1: Positive blood culture amongst neonatal participants
- Primary outcome for Phase 3: Clinician (specialist neonatal or paediatric doctor) diagnosis of sepsis amongst neonatal participants as documented in clinical notes or discharge letter
- Clinical features of neonatal sepsis as listed in GAIA neonatal infections case definition
- Admission to neonatal unit
- Readmission to hospital in first 28 days amongst neonatal participants
- Death before 28 days of age
- Sensitivity, specificity, positive and negative predictive value of risk stratification model for participants in Kampala and Harare

Using machine learning to model early-onset neonatal sepsis risk in Uganda (NeoRisk)

5 STUDY DESIGN and METHODS of DATA COLLECTION AND DATA ANALYSIS

There will be three main phases to this study, which is an observational cohort study.

Using machine learning to model early-onset neonatal sepsis risk in Uganda (NeoRisk)

Phase 1 will take place at Kawempe Hospital in Kampala, Uganda. Participants will be recruited from labour wards by study staff, and interim analysis will be completed after recruitment of 10% of the total sample. See section 7.3 for further details.

Data will be collected via an online CRF, including the factors listed in the table in Section 3.

Additionally:

- All neonates within the study will have a **neonatal venous blood sample** taken for culture by designated study staff
 - This must be taken before administration of antibiotics or within 48 hours of birth, whichever is sooner, and regardless of whether the neonate is being investigated and treated for sepsis.
- **Postnatal information** will be collected via telephone at 1 month including maternal and infant outcome, hospital readmission or clinical illness, and vaccines given

All data will be checked for quality control by a member of the study team.

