A blood culture will be taken from all neonatal participants at birth, prior to starting antibiotic treatment wherever safe to do so. The volume of blood taken for culture must be 1-2ml and will be verified by weighing blood culture bottles. Training will be provided to paediatric and study teams on blood culture sampling methods, including adequate cleaning of the skin prior to sampling. Feedback on sample volumes and contamination rates (see section 7.3 for definition) will be fed back to paediatric consultants, and additional staff training offered. Where sample is remaining after 3ml is added to the culture bottle, the excess will be retained as a blood spot sample for use in future ethically approved research, where the participant has consented to this.

The results of the microbiological tests will be communicated to the participant's clinical team in real time – see section 7.3.4 for further details. Clinician diagnosis of sepsis will be recorded where a clinician of registrar level or above has recorded a diagnosis of sepsis within 48 hours of birth. To reduce the subjectivity of this measure, GAIA level of certainty for a diagnosis of sepsis will also be assessed (35) and the level of diagnostic certainty recorded (1-5, as per GAIA criteria). Medical records are recorded on paper at Kawempe Hospital, before being coded into an electronic medical record by data clerks. PDF scans of medical records will be available where detailed review is required.

All participant data will be collected by trained study staff, and recorded into an online CRF hosted on REDCap, a secure web application. No patient identifiable data will be stored on the main REDCap database. See section 8.6 for further details of data management plans.

The postnatal information will be completed via a telephone call at 28 days post-delivery, made by study staff. Participants' contact number, a contact number for their partner, and a contact number for a second friend or family member will be taken at recruitment to minimise loss to follow up due to changes to mobile telephone number. Participant identity will be confirmed using three factors (date of birth, full name, address/village). The following information will be collected:

- Health status of mother and baby
- Any visits to medical care for the neonate
 - If attended or admitted to Kawempe hospitals, these electronic medical records will be reviewed by study staff

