The TRIPOD (Transparent reporting of a multivariable prediction model for individual prognosis or diagnosis) statement have been followed in the design of this study and will be followed in its reporting(42). Adjustments will be made as necessary with the release of upcoming artificial intelligence-specific guidelines.

Data analysis

Phase 2 will constitute the main data analysis for data from Uganda.

There will be two main streams to data analysis, which will be completed using R and in collaboration with the Advanced Research Computing Centre at UCL.

1. Machine learning analysis:
 - a. Data from Phase 1 will form a ‘training data set’, with 20% reserved for testing and validation, and be fed into a pre-programmed machine
 - b. Previous methods used for sepsis prediction that will be investigated include gradient tree boosting and neural networks
 - c. Bootstrapping will be considered
 - d. Determination of the exact machine learning model will depend on the data obtained, but the following will be considered:
 - i. Weighted inputs: Allows scaling of measurements
 - ii. Conformal prediction: Allows the machine to determine how uncertain its prediction is, based on distribution of data it has, and missing data
 - iii. Recurrent neural networks: Allows the machine to recognise time-dependent patterns
 - iv. Gradient descent: A method of ‘training’ a machine to minimise the error between prediction and reality by gradually adjusting its weights
2. Traditional logistic regression will be used to identify risk factors associated with clinical and microbiological diagnoses of neonatal sepsis. Although the principal model will be created using machine learning techniques, logistic regression will be

Using machine learning to model early-onset neonatal sepsis risk in Uganda (NeoRisk)

used as a second check of results and to provide additional context with which to interpret the machine learning model

For **Phase 3**, data will be inputted to the machine learning model from Phase 2, and the sensitivity, specificity, positive predictive and negative predictive values calculated, as well as the AUC value.

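### No prediction time or predictor cut-off is stated, so clinical signs recorded up to 72 h of life can enter the model after the culture is drawn or the diagnosis window has closed

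*Combined protocol and SAP*

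**What the plan says.** **Inputs.** The Section 3 table of risk factors has a row "Clinical signs of sepsis or meningitis within first 72h of life" with nine signs under it, marked as established. They stand beside Apgar scores and method of feeding. One of the nine, jaundice, carries its own limit of 24 h. Section 5 says the table's factors are collected on the electronic case report form. Its data analysis part makes the Phase 1 data a training set, "with 20% reserved for testing and validation, and be fed into a pre-programmed machine". The data protection assessment (Appendix 3) says the table's fields are collected because all may relate to the infant's risk of early-onset sepsis. Section 5 also says Phase 3 collects the same data as Phase 1.

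**Outcomes.** The Phase 1 primary outcome is a positive blood culture (Section 4.2). Section 5 gives its timing twice: "This must be taken before administration of antibiotics or within 48 hours of birth, whichever is sooner", and then "A blood culture will be taken from all neonatal participants at birth, prior to starting antibiotic treatment wherever safe to do so". It is taken "regardless of whether the neonate is being investigated and treated for sepsis". Clinician diagnosis, a secondary outcome in Phase 1, counts where a clinician of registrar level or above "has recorded a diagnosis of sepsis within 48 hours of birth". The Phase 3 primary outcome is senior clinician diagnosis in the same 48 h. Section 3 defines early-onset sepsis as "those infections presenting within 72 hours of life".

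**Feedback.** Culture results go to the clinical team in real time (Section 5). Samples are processed within 12 h of collection and incubated for 36 h (Section 7.3.4).

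**Not stated.** No section gives a prediction time, a list of predictors kept apart from outcomes, a time stamp for signs, or a rule that removes signs recorded after the culture or the diagnosis.

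**The concern.** A prediction model should use only what is known when the prediction is made. Here the window for one group of candidate inputs closes later than the outcomes those inputs would predict. Three separate problems can follow.

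- **Late signs.** A sign first seen after the culture was drawn, or after 48 h, is not prior information about that outcome.
- **Feedback.** Once a positive culture has been reported, clinicians may look for signs, and record them, differently.
- **Incorporation.** A clinician diagnoses sepsis largely from such signs. If they are also inputs, the model is partly predicting its own ingredients.

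The reserved 20% of Phase 1 data would not reveal the first two problems, because those records are collected in the same way as the training records. Phase 3 would not reveal the third, because its primary outcome is the clinician's diagnosis. Sensitivity, specificity, predictive values and AUC, which are what the study will report, cannot be interpreted unless the reader knows when the inputs were available.

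**Working it through.** The plan gives no figure for this point, so there is none to reproduce. The check compares the stated time windows and then adds an illustration under assumed values.

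**1. Sign window against diagnosis window.** Signs run to 72 h (Section 3) and diagnosis closes at 48 h (Section 5). 72 − 48 = 24 h, and 24/72 = one third of the sign window lies after the diagnosis outcome has closed.

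**2. Sign window against culture.** For a draw at t hours, 72 − t hours of the sign window remain. Incubation is complete at t + 36 to t + 48 h, assuming 0 to 12 h from collection to processing and then 36 h of incubation. The time to report is not given; a culture may flag positive earlier, and identification takes longer.

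| Draw (h) | Sign window left after draw (h) | Incubation complete (h) | Before 72 h? |
|---|---|---|---|
| 0 | 72 | 36–48 | yes |
| 24 | 48 | 60–72 | yes, or just at 72 h |
| 48 | 24 | 84–96 | no |

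Feedback from a completed culture is thus possible for early draws and not for draws near 48 h. Signs that post-date the draw are possible for all of them.

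**3. Which problem applies to which outcome.**

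| Outcome | Sign can post-date it | Sign can help define it |
|---|---|---|
| Phase 1 culture (primary) | yes | no: drawn from every neonate whatever the suspicion |
| Phase 1 clinician diagnosis (secondary) | yes | yes |
| Phase 3 clinician diagnosis (primary) | yes | yes |

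**4. Illustration (every value assumed, none from the documents).** Take a normal risk score with AUC = A at birth. Add one independent sign with frequency p1 in cases and p0 in non-cases, combined by likelihood ratio. Let d = √2·Φ⁻¹(A) and w = ln(p1/p0) − ln((1 − p1)/(1 − p0)). Then

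AUC = [p1·p0 + (1 − p1)(1 − p0)]·A + p1(1 − p0)·Φ(d/√2 + w/(d√2)) + (1 − p1)p0·Φ(d/√2 − w/(d√2)).

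With A = 0.70, p1 = 0.5 and p0 = 0.2: d = 0.742 and w = ln 4 = 1.386. So AUC = 0.5 × 0.700 + 0.4 × 0.968 + 0.1 × 0.213 = 0.350 + 0.387 + 0.021 = 0.758. A simulation of the same set-up gave 0.759.

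| A at birth | 30% / 30% | 50% / 20% | 70% / 20% | 90% / 20% |
|---|---|---|---|---|
| 0.65 | 0.65 | 0.73 | 0.81 | 0.89 |
| 0.70 | 0.70 | 0.76 | 0.83 | 0.90 |
| 0.75 | 0.75 | 0.79 | 0.85 | 0.92 |

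A sign equally common in both groups adds nothing, and an informative one raises the AUC. The table shows the gain from any informative sign, including one properly recorded at one hour. It does not isolate the part due to late recording.

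**The case against.** The other side has four good arguments, and each limits the point.

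- **Model entry is inferred.** A reader might take the plan to say that 72 h signs are model inputs. It does not say so outright. The table is introduced as a list of fields to collect, and Section 5 leaves the model's factors to be determined. The signs also have other documented uses: GAIA features are a listed outcome, GAIA certainty is graded, and Objective 3 studies clinical features apart from the risk model of Objective 2. This stands. It does not remove the gap, because nothing keeps the signs out, and an open input list is the reason to set the rule before modelling.
- **The Phase 1 culture is not defined by signs.** A reader might infer circularity there too. Universal sampling rules it out, and only timing remains.
- **One hour is not the stated time of use.** Section 1 says "Ideally, antibiotics should be given within an hour of birth in cases of suspected early-onset sepsis", and a reader might conclude that a model with later signs could never be used. That sentence is background on treatment. Section 2 also names close monitoring, earlier discharge of low-risk neonates and service planning, where some later information may properly be known. Some listed signs, such as respiratory distress, can be present at birth. A model with signs is a legitimate design if its inputs are timed.
- **The AUC figures do not measure the bias.** They rest on assumed frequencies, and Section 3 itself stresses that neonatal signs are nonspecific. This stands in full.

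**Conclusion.** The point holds in this form: the plan states neither a prediction time nor a predictor cut-off, and as written it lets signs recorded after the culture draw, after a reported result, or after the 48 h diagnosis cut-off enter the model. Accuracy can then be inflated. Validation against clinician diagnosis can also be partly circular, and in Phase 3 that is the primary outcome of the only external test.

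The documents support the windows: one third of the sign window lies after the diagnosis cut-off, and 24 to 72 h of it lies after the draw. They do not support a figure for the inflation. It depends on which signs are kept, when they are recorded and how informative they are. Nor do they support saying that accuracy is inflated as a matter of fact. The conclusion assumes only that the table's fields are candidate inputs, which is the natural reading of Sections 3 and 5 and Appendix 3 taken together.

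This is more than missing detail, because following the text literally is what would produce the fault.

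**What to change.** - State a prediction time for the principal model. Admit only inputs known by that time and before both the culture draw and any clinician diagnosis.
- Keep later signs for GAIA grading and Objective 3.
- Record the time of each sign where possible. Where no time is available, leave that sign out of the principal model. This may affect neonates already enrolled: Section 5 anticipated Phase 1 for January to July 2024, and hospital records are on paper and coded later.
- Report the model with and without signs. Treat Phase 3 results for the version with signs as subject to incorporation bias. Time-stamping does not cure this, because a sign seen before the diagnosis can still be a reason for it.
- Use the same input list in Phase 3.
- Reconcile the two statements of culture timing in Section 5, and the 48 h diagnosis window with the 72 h definition of early-onset sepsis.

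**Cost.** Wording in the analysis plan, an added time field on the case report form, and probably a lower headline AUC. The time field is the urgent part, because times not recorded during collection may not be recoverable.
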